2.3 Endpoints

2.3.1 Definition:

Safety: Gleolan®-related adverse events will be recorded using standardized toxicity criteria and known side effect profile up to 6 weeks after surgery. Monitoring for adverse events will take place before and after Gleolan® administration, 48h after surgery, 2 weeks and 6 weeks postoperatively.

2.3.1 Primary endpoint:

The feasibility of using oral Gleolan® as an adjunct diagnostic imaging tool for malignant tumor tissue fluorescence will be primarily assessed by computing sensitivity of intraoperative Gleolan® induced PPIX tissue fluorescence.

PPIX tissue fluorescence will be defined categorically as "no" (score 0), "low" (score 1), "medium" (score 2), and "high" (score 3) by operative surgeon, and images will be recorded. For purposes of computing measures of diagnostic performance a score of 0 will be considered a negative test result and a score of 1, 2 or 3 will be considered a positive test result.

2.3.2 Secondary endpoints:

2.3.2.1 The diagnostic performance of Gleolan® will further be assessed by computing measures of specificity, positive predictive value (PPV), negative predictive value (NPV), and accuracy of intraoperative Gleolan® induced fluorescence with a score of 0 will be considered a negative test result and a score of 1, 2 or 3 will be considered a positive test result.

2.3.2.2 Incidence of Gleolan®-related adverse events

3.0 PATIENT ELIGIBILITY

3.1 Inclusion Criteria

- 3.1.1 Subjects included in this trial must have had documentation of a new or recurrent head and neck or skull base tumor for which surgical resection is indicated and has been planned. These patients will include those with newly diagnosed or recurrent malignancies.
- 3.1.2 Age 18-80
- 3.1.3 Karnofsky score >60%
- 3.1.4 Subjects must have normal organ and marrow function as defined below:

- leukocytes ≥ 3,000/mcL - absolute neutrophil count ≥ 1,500/mcL - platelets ≥ 100.000/mcl

- total bilirubin within normal institutional limits

- AST(SGOT)/ALT(SPGT) \leq 2.5 X institutional upper limit of normal

- creatinine within normal institutional limits

OR

Creatinine clearance >60 mL/min/1.73m2 for patients with creatinine levels above institutional normal as defined per institution.

- 3.1.5 The effects of Gleolan® (5-ALA) on the developing human fetus are unknown. For this reason, women of child-bearing potential and men must agree to use adequate contraception (hormonal or barrier method of birth control; abstinence) prior to study entry and for the duration of study participation. A pregnancy test will be performed for all women of childbearing ability prior to surgery (see Exclusion Criteria below). Should a woman become pregnant or suspect she is pregnant while participating in this study, she should inform her treating physician immediately.
- 3.1.6 Ability to understand and the willingness to sign a written informed consent.

3.2 Exclusion Criteria

- 3.2.1 Patients with non-resectable tumors or not deemed surgical candidates
- 3.2.2 History of allergic reactions attributed to compounds of similar chemical/biologic composition to ALA.
- 3.2.3 Personal or family history of porphyria
- 3.2.4 Uncontrolled concurrent illness including but not limited to: ongoing or active infection, symptomatic congestive heart failure, unstable angina pectoris, cardiac arrhythmia, or psychiatric illness//social situations that would limit compliance with study requirements

- 3.2.5 Women who are pregnant or become pregnant will be excluded from the trial as it is unknown if ALA is teratogenic or has abortifacient effects. Because there is an unknown but potential risk for adverse events in nursing infants secondary to treatment of the mother with 5-ALA breastfeeding should be discontinued if the mother is treated with 5-ALA.
- 3.2.6 Prior history of GI perforation, diverticulitis, and or/peptic ulcer disease

4.0 TREATMENT PLAN

4.1 Treatment Dosage and Administration

- 4.1.1 Treatment will be administered on an inpatient basis. This does not pose a financial burden to the subject as pre-operative care provides for admission to hospital. One-time, single-dose oral administration of Gleolan® (5-ALA) is planned (20mg/kg). No investigational or commercial agent or therapies other than those described below may be administered with the intent to treat the patient's malignancy prior to surgery and patients will not be part of any other clinical trial at the time of this surgery for anything, not just the identified, malignant tumor.
- 4.1.2 Gleolan® (5-ALA) 20mg/kg will be reconstituted in the minimum volume of sterile water and may be mixed with a clear liquid or apple fruit juice before being administered in a single oral dose approximately 3 hours (3-5h) prior to scheduled surgery. This one-time single dose administration precludes the need for intra-patient dose modification or delay. In the event of emesis of the product, the dose will not be repeated.

Gleolan® (5-ALA) is presented as a powder for oral solution in 60 ml colorless glass vials. The formulation contains 1.5 g 5-aminolevulinic acid hydrochloride corresponding to 1.17 g of 5- aminolevulinic acid. No other ingredients are used besides the clear liquid or apple juice used to mix with at time of consumption. No impurities have been identified. Details on the manufacturing method, validation of the process as well as in process controls are available and are on file with the FDA. The drug product is manufactured according to a documented, validated process that has given comparable results in the production of both pilot and large scale batches. The specification and release tests for the drug product are in compliance with both Pharmacopia European and current guidelines. Where applicable, analytical validation has been performed.

Limits for impurities and possible degradation products are set according to the results reported for the batches used for relevant toxicological and clinical testing taking into account the proposed route of administration as well as the relevant guidelines. The specifications and the routine release tests are adequate to control the quality of the drug product and are on file with the FDA. Stability test results after 36 months storage justify a shelf-life of 36 months when stored at $25^{\circ}\text{C} \pm 2^{\circ}\text{C}$. After reconstitution, the in-use shelf-life is 24 hours when the solution is stored at room temperature. In conclusion, the data are complete and satisfactory, ensuring the reproducible manufacturing of a product of good quality.

The specification and release tests for the drug substance are in compliance with Pharmacopia European and current guidelines. The analytical methods are either pharmacological methods or well validated. Stability results after both

accelerated and long term testing indicate that the drug substance 5-aminolevulinic acid hydrochloride can be considered stable. The stability data support a satisfactory retest period of 3 years when stored at -20 °C in the proposed container. The aseptic manufacturing process of the drug product consists of four steps: compounding, filtration, filling and lyophilisation. The validation of the manufacturing process is satisfactory and relevant in-process controls are performed. The synthesis of the drug substances consists of three stages, for which the potential content of each vial is intended to be reconstituted in 50 ml water or apple juice. One ml of the reconstituted solution contains 23.4 mg of 5-aminolevulinic acid, corresponding to 30 mg 5-aminolevulinic acid hydrochloride. The closure consists of colorless glass vial (Type II, Ph Eur) and bromobutyl-rubber stopper 20 mm (Type I, Ph Eur) and a flip cap top.

The oral solution is intended for single (partial) use. 5-aminolevulinic acid hydrochloride is administered orally to adult patients with head and neck malignancy prior to tumor removal by surgery. 5- Aminolevulinic acid is a prodrug that is metabolized intracellularly to form the fluorescent molecule protoporphyrin (PPIX), which is selectively accumulated in tumor cells and epithelial tissue. Following excitation with blue light (λ = 400 – 410 nm) the PPIX, which has accumulated selectively in the malignant tissue, the tumor emits a red-violet light (red-light fluorescence). Tumor resection is extended as the surgeon is able to identify malignant tissue as differentiated from normal tissue after administration of 5-aminolevulinic acid (Stummer et al. 2006, 2010).

4.2 Toxicities and Dosing Delays/Dose Modifications

Any patient who receives treatment on this protocol will be evaluable for toxicity. Each patient will be assessed for the development of toxicity according to the Time and Events table (See section 5.4). Toxicity will be assessed according to the NCI Common Toxicity Criteria for Adverse Events (CTCAE), version 4.0. Dose adjustments should be made according to the system showing the greatest degree of toxicity.

4.3 Concomitant Medications/Treatments

Compounds of similar chemical/biologic composition to 5-ALA are prohibited. Patients should refrain from use of other phototoxic substances (e.g. tetracyclines, sulfonamides, fluoroquinolones, hypericin extracts) for 72h after administration. Patients should avoid exposure of eyes and skin to strong light sources (e.g. operating illumination, direct sunlight or brightly focused indoor light) for 24h after 5-ALA administration. Patients should not be exposed to any photosensitizing agents up to 2 weeks after 5-ALA administration.

Within 24h after 5-ALA administration, other potentially hepatotoxic medicinal products should be avoided.

In patients with pre-existing cardiovascular disease, concomitant blood pressure medications should be used cautiously as 5-ALA has been shown to decrease systolic and diastolic blood pressure, pulmonary artery systolic and diastolic pressure, and vascular resistance.

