1.2.1 Pharmacology

Aminolevulinic acid (ALA) is the first step in the biochemical synthesis of hemoglobin in animals. Aminolevulinic acid is a metabolic precursor of protoporphyrin IX (PPIX), which is a photosensitizer. The metabolism of 5-ALA is normally tightly controlled by feedback inhibition reflecting likely the intracellular levels of hemoglobin. The feedback control is through the enzyme, 5-ALA synthetase. Exogenous oral 5-ALA, bypasses this feedback inhibition and PPIX accumulates to be converted into heme. Excess 5-ALA and PPIX are thus excreted.

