1.2.2 Pharmacokinetics

General characteristics

5-ALA is soluble in water and well absorbed through the GI tract. After ingestion, 5-ALA dosing at 20mg/kg, is metabolized to fluorescent porphyrins, predominantly protoporphyrin IX (PPIX).

Absorption

5-ALA HCl as an oral solution is rapidly and completely absorbed and peak plasma levels of 5-ALA are reached 0.5-2 hours after oral administration of 20 mg/kg body weight. With a terminal half-life of 45 minutes, plasma levels return to baseline values 24 hours after administration of an oral dose of 20 mg/kg/ body weight. 5-ALA is generally given on an empty stomach prior to induction of anesthesia.

Distribution and Biotransformation

Oral 5-ALA is metabolized by the liver, kidney, endothelial cells, skin, as well as by malignant gliomas (WHO grade III and IV) and metabolized to fluorescent PPIX. The plasma protein binding of 5-ALA is 12%. Four hours after oral administration of 20 mg/kg/body weight 5-ALA HCI, the maximum PPIX plasma level is reached. PPIX plasma levels rapidly decline and are not detectable 48 hours after administration. In a human pharmacokinetic study (N= 6) using a 128 mg dose of sterile intravenous 5-ALA HCI and oral 5-ALA HCI (equivalent to 100 mg 5-ALA) in which plasma 5-ALA and PPIX were measured, the mean half-life of 5-ALA was 0.70 \pm 0.18 h after the oral dose and 0.83 \pm 0.05 h after the intravenous dose. The oral bioavailability of 5- ALA was 50-60% with a mean Cmax of 4.65 \pm 0.94 μ g/mL. PPIX concentrations were low and were detectable only in 42% of the plasma samples. PPIX concentrations in plasma were quite low relative to 5-ALA plasma concentrations, and were below the level of detection (10 ng/mL) after 10 to 12 hours.

At the oral 5-ALA dose of 20 mg/kg/body weight, tumor:normal brain fluorescence ratios are usually high and provide for 'blue light' visualization of fluorescent tumor tissue as red-violet for at least 9 hours. Besides tumor tissue, faint fluorescence of the choroid plexus has been reported. 5-ALA is also taken up and metabolized to PPIX by other tissues, e.g. liver, kidneys or skin (see section 4.4).

Elimination

[figure not shown]
5-ALA is eliminated quickly. Approximately 30% of an orally administered dose of 20 mg/kg/body weight is excreted unchanged in urine within 12 hours.

Linearity/non-linearity

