Webber et al. observed that almost one-quarter of all patients who received 5-ALA had at least one abnormality in liver function tests. More patients receiving low doses (< 30 mg/kg) developed abnormalities than those receiving high doses. Significant variations in the time of appearance of the abnormalities were also noted (12 to 120 hr. postoperatively). In all cases, liver function tests returned to normal within 2 months after receiving 5-ALA.

In a single-arm European study including 21 healthy male volunteers, erythema of the skin was provoked by direct exposure to ultraviolet light up to 24 hours after oral application of 5-ALA HCI (20 mg/kg/ body weight). PPIX photosensitization manifests as an unpleasant pricking, itching, or burning sensation under the skin after exposure to the sun. A systemic load above 10 mg/kg is required to develop skin photosensitization which lasts from approximately 24 to 48 hours following 5-ALA administration. It is for this reason that patients will be kept in subdued light conditions for up to 48 hours following surgery.

Possible drug-related mild nausea was reported in 1 of 21 volunteers. In another single-center study, 21 patients with malignant glioma received 0.2, 2, or 20 mg/kg body weight 5-ALA HCl followed by fluorescence-guided tumor resection. The only adverse reaction reported in this trial was one case of mild skin erythema occurring in a patient treated with the highest dose.

In a single-arm European study including 36 patients with malignant glioma, drug-related adverse events were reported in 4 patients (one patient: mild diarrhea, one patient: moderate hypesthesia, one patient: moderate chills, and one patient: arterial hypotension) 30 minutes after dosing with 5-ALA HCl20 mg/kg body weight prior to fluorescence-guided resection. Follow-up time was 28 days.

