4.4 Other Modalities or Procedures

Fluorescence-guided resection will be performed using the standard surgical operating

microscope. The surgical operating microscope will be adapted with a filter set intended to visualize fluorescence excitation in the wavelength range from 390nm to 440nm and for observation in the 600-700nm range. The adaptation includes standard white light emission source and a combination of excitation and observation low and high pass optical filters with slightly overlapping transmission integrated into their optical configuration. The proposed filter set is commercially available globally. A small fraction of excitation light is remitted from the tissue, which then generates a blue tone contrast from the healthy brain anatomy in contrast to the bright red. 5-ALA induced PPIX fluorescence. Thus, there are two light sources to illuminate the resected field: White light phase and Blue light phase. During the white light illumination, an attenuator reduces irradiance to approximately 50% to minimize the need for illumination adjustment. During the blue light phase, an electromagnetic filter switch is used to introduce a dielectrically coated observation filter with a 600-700nm wavelength into the light paths of the surgical microscope. These filters transmit tumor associated red PPIX fluorescence and a portion of backscattered normal tissue blue excitation light which does not fluoresce. A camera system on the microscope is used to record 5-ALA/PPIX red fluorescence.

Gleolan® (5-ALA) will be reconstituted in the minimum volume of sterile water and may be mixed with a clear liquid or apple fruit juice before being given orally approximately 3 hours (3-5h) prior to scheduled surgery. Image-guided microsurgical resection of the tumor will be undertaken as per operator preference. Following standard surgical entry, further tumor resection will be performed by switching to the microscope fluorescence 'blue light' mode.

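### Section 4.3 ends strong-light avoidance 24 hours after dosing, the low end of the photosensitization range in 1.2.3, and does not match the 48-hour post-surgery commitment there; one limit on one clock would fix it

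*Combined protocol and SAP*

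**What the plan says.** Section 4.3 (Concomitant Medications/Treatments) asks patients to keep eyes and skin away from strong light. Its examples and time limit read "e.g. operating illumination, direct sunlight or brightly focused indoor light) for 24h after 5-ALA administration". The same section bars other phototoxic substances for 72 hours and photosensitizing agents for up to 2 weeks; those limits concern drugs, not light.

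Section 1.2.3 (Toxicity) says that a load above 10 mg/kg produces "skin photosensitization which lasts from approximately 24 to 48 hours following 5-ALA administration", and continues: "It is for this reason that patients will be kept in subdued light conditions for up to 48 hours following surgery". The trial dose is 20 mg/kg (4.1.1).

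Sections 5.2 and 5.3 and the table in 5.4, which list what is done at each visit, contain no light precaution. Section 4.3 does not refer to 1.2.3. Section 7.1.7 does: it names photosensitivity among the side effects and sends the reader to 1.2.3 for the full profile.

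**The concern.** The treatment plan and the toxicity section give different end points for what looks like the same hazard, and they count from different events: dosing in 4.3, surgery in 1.2.3. The shorter limit is in the treatment plan, and it equals the shortest duration that 1.2.3 allows for photosensitization. From 24 hours on, 4.3 no longer restricts even direct sunlight, while 1.2.3 may still call for subdued light.

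What is at stake is a patient-safety instruction. Someone working from 4.3 could end strong-light avoidance while, by the protocol's own account, the patient may still be photosensitive.

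**Working it through.** The plan gives no calculated figure to reproduce here. The check puts the stated windows on one clock and then sets the evidence on duration side by side.

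**Inputs**
- Strong-light avoidance: 24 h after dosing (4.3).
- Duration of photosensitization: about 24 to 48 h after dosing (1.2.3).
- Subdued light: up to 48 h after surgery (1.2.3).
- Interval T from dosing to surgery: the drug is "given orally approximately 3 hours (3-5h) prior to scheduled surgery" (4.4), and surgery may start as late as 8 h after dosing (4.5). So T is 3 to 5 h as planned and 8 h at most.
- Dose against threshold: 20 / 10 = 2, so the trial dose is twice the load that 1.2.3 gives for skin photosensitization.

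**Part of the stated range that 4.3 alone leaves uncovered**

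Duration minus 24 h: 24 − 24 = 0 h at the short end and 48 − 24 = 24 h at the long end.

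**The two limits on a common clock, counting surgery from its start**

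| T | 4.3 limit, hours after surgery starts (24 − T) | 1.2.3 limit, hours after dosing (48 + T) | Difference (48 + T − 24) |
|---|---|---|---|
| 3 h | 21 | 51 | 27 |
| 5 h | 19 | 53 | 29 |
| 8 h | 16 | 56 | 32 |

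If 1.2.3 is counted from the end of surgery, the operating time is added to the last two columns. The documents do not give that time.

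**Does the 1.2.3 limit cover the range?** Yes, if applied in full. It ends 51 to 56 h after dosing, which is 3 to 8 h past the 48 h upper end.

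**Evidence on duration in the documents**
- For 24 h: in 21 volunteers at 20 mg/kg, "erythema of the skin was provoked by direct exposure to ultraviolet light up to 24 hours after oral application" (1.2.3). For 5-ALA itself, "plasma levels return to baseline values 24 hours after administration of an oral dose" (1.2.2).
- For 48 h: the agent that matters is the metabolite. Section 1.2.1 says "Aminolevulinic acid is a metabolic precursor of protoporphyrin IX (PPIX), which is a photosensitizer", and 1.2.2 says "PPIX plasma levels rapidly decline and are not detectable 48 hours after administration". Section 1.2.3 also reports, from the phase III glioma trial, one mild photosensitivity 48 hours after surgery among 201 recipients.
- Limits of this evidence: the pharmacokinetic values are plasma, not skin. The earlier loss of detectable PPIX in 1.2.2 (after 10 to 12 h) comes from a 128 mg dose and does not carry over to 20 mg/kg.

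The evidence is mixed. It does not show that 24 h is wrong for strong light, but it gives no reason to stop at the low end of the protocol's own range.

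**The case against.** The strongest reply is that the hazard is already covered. The two precautions differ in kind, strong light in one section and subdued light in the other, and can be followed together as layers. Section 1.2.3 is worded as a commitment, 9.6 requires the protocol to be followed as written, and 7.1.7 directs readers to 1.2.3. The volunteer data give 24 hours some support, dosing is inpatient (4.1.1), and an examination with adverse-event monitoring falls within 48 hours (5.2.3). The 72-hour and 2-week drug limits in 4.3 also run past 24 hours.

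Most of this stands. A reader might infer that the protocol leaves patients unprotected after 24 hours, or that 4.3 ends all precautions then. The documents do not support that: 1.2.3 followed in full covers the whole range, and only strong-light avoidance in 4.3 lapses.

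The reply does not close the matter. The wording in 1.2.3 sets a ceiling, so it guarantees no minimum. Nothing says that the two rules are layered. The visit procedures in section 5 carry no light step that would settle which rule to apply.

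**Conclusion.** The mismatch is real and minor. Section 4.3 stops at the low end of the 24-to-48-hour range and ends 27 to 32 hours before the 1.2.3 limit, counted from the start of surgery. The uncovered part is 0 to 24 hours, and it arises only where 4.3 is applied alone or subdued light is ended early within the ceiling.

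The documents do not allow a count of extra skin reactions under the shorter limit, and none should be inferred. The skin reactions reported in glioma patients in 1.2.3 are one mild erythema among 21 patients in a dose-comparison study, at the highest dose (20 mg/kg), and the one mild photosensitivity among 201 recipients. Nor should a reader infer any effect on the sensitivity estimate, the sample size or the adverse-event analysis.

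The arithmetic assumes that surgery starts 3 to 8 hours after dosing. Consent pages are not in this copy, so light instructions given to patients could not be checked. This is a cheap improvement, not a necessary correction.

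**What to change.** Replace the 24-hour limit in 4.3 with one limit on one clock, and use the same wording in 1.2.3. For example: *Avoid strong light to eyes and skin until 48 hours after surgery, and in no case for less than 48 hours after the dose, except for the illumination needed for the operation.* Say whether the 48 hours run from the start or the end of surgery, and list the precaution in 5.2.

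Three features of the wording matter:
- **Surgery clock.** Changing only the number in 4.3 to 48 hours after dosing would cover the range, but it would end 40 to 45 hours after surgery starts (48 − 8 to 48 − 3), which is 3 to 8 hours before the 1.2.3 limit, and two clocks would remain.
- **Floor after dosing.** Section 4.5 allows a dosed patient not to proceed to fluorescence-guided surgery. If no operation follows, a limit counted from surgery has no starting point.
- **Operating-light exception.** Section 4.3 lists operating illumination among the sources to avoid, yet the operation itself falls inside the window.

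The cost is one sentence in 4.3, matching words in 1.2.3 and one line in 5.2. For patients it means about one more day of strong-light avoidance where only 4.3 was being applied (27 to 32 hours from the table, plus operating time if counted from the end of surgery), and little or none where the full 48 hours of 1.2.3 is already followed.
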